**b) Sustainability of the effect at month 12**

HINT in quiet conditions performed at month 6 in English speakers will be compared to the result at month 12 to assess the sustainability of the effect over time. A one-sided ( $\alpha = 0.025$ ) t-test for paired samples will be used for that purpose.

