## 1. SUMMARY

Title	"The Neuro Zti Cochlear Implant System Efficacy and Safety in Adults"
Sponsor	Oticon Medical
Investigator Coordinator	[name] (Canada)
Phase and Design	Multinational, multicenter, prospective, open label, single arm.
Study description	
The new cochlear implant system (CIS) is indicated in individuals with serious hearing disabilities who do not obtain benefit from appropriately fitted hearing aid(s). Cochlear implant surgery is safe, but as with any surgery, possible issues or device related issues may occur. The risk benefit balance is well known in cochlear implantation.
 
The aim is to assess the efficacy and the safety of this new CIS in adults.

Primary objectives	
To demonstrate the efficacy of the new CIS through improvement of speech performance in quiet conditions after CIS implantation.
 
To evaluate the safety of the CIS.

Secondary objectives	
To assess the device effect with speech performance in noise.
 
To show sustainability of the device effect in quiet and in noise in time and after 12 months of use.
 
To assess whether the time of course of the response follow the same tendencies (increase, decrease, slope inversion) in the three languages in quiet and noise conditions.

Primary endpoints	
HINT score in quiet (HINT-Q) at 6 months of device use.
 
Major complications incidence rate at 12 months of device use.

Secondary endpoints	
HINT in noise (HINT-N) scores at 3, 6 and 12 months of device use
 
HINT-Q scores at 3 months and at 12 months,
 
Electrodes impedance at each visits
 
ECAP at each visit

Inclusion & exclusion criteria	
Inclusion:
 
 
- <math>\geq 18</math> y.o.,
 
- Bilateral severe-to-profound sensorineural hearing loss,
 
- Post-lingual deafness
 
- Limited benefit from appropriately fitted hearing aid(s),
 
- Primary implantation,
 
- No anatomic contraindications,
 
- Fluent in local language,
 
 
Exclusion:
 
 
- Medical conditions that contraindicate undergoing surgery,
 
- Psychologically unsuitable,
 
- Unwillingness or inability to comply with all investigational requirements.
 

Investigational medical device	Neuro CIS, with Neuro Zti implant and Neuro One processor

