#### **2.4.2 Secondary objectives**

Secondary objectives are:

- To establish the time course of the change from baseline of HINT-Q score in English speaking patients and in all patients to assess the efficacy of the device in a dynamic perspective.
- To test the sustainability of the device effect in Quiet conditions (HINT-Q) through the comparison of the scores at month 6 and month 12 in English speaking patients and possibly in all patients in case of absence of significant language effect in the improvement from baseline.
- To assess the performance of device in noise using HINT-N test in English speaking and possibly in all patients at 3, 6 and 12 months compared to baseline (best-aided condition). The comparison of the score at 6 and 12 months will indicate the sustainability of the effect.
- To evaluate the trend of device efficacy in quiet and noise conditions across English speaking, French speaking and Danish speaking patients.

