## **3.6 Study Outcome Evaluations**

### **3.6.1 Study Endpoints**

#### **3.6.1.1 Primary Endpoints**

Previous studies analyzed their samples based on fixed time intervals after implantation, usually 1, 3 and 6 months, then annually thereafter. After 6 months of CI experience outcomes appear to be stable with the majority of users reaching a performance plateau. Massa et al. [5] observed a performance plateau at a median of 4.7 months post-implantation. Similar results were reported by Bradley et al. [8] demonstrated a plateaued performance around 6 months in a sample of 55 patients. In Dillon et al. study [9] the adults tested with HINT in quiet at 70 dB experienced growth in speech perception within the first 6 months and remained stable thereafter. This plateau at 6

months is generally consistent with findings from others previous research with other speech discrimination tools, as Lenarz et al. study [7] using German language tests in a large cohort.

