**c) Difference in the time course of HINT-Q responses across languages**

The FAS including all patients instead of the subset of English speaking patients will be used in these secondary analyses. A mixed model for repeated measures will be fitted using the change from baseline to M3, M6 and M12 in the HINT-Q score as the responses and the following covariates or terms: the visit (M3, M6 and M12, fixed effect), the patient (random effect), the language (fixed effect) and the interaction between visit and language. The variance covariance matrix will be unstructured. If the p value of the interaction is below 0.15 then a signal of potential interaction is detected and the time course of speech performance is possibly dependent upon the language. Regardless the p value of interaction a graph will present the time course of the response for each language.

A series of contrasts will be performed to estimate and test:

1) The difference between languages in the change from baseline at each time point.

The estimate and test at M6 will be the most supportive result.

2) The overall mean change from baseline at each time point. The test against no change will be performed. Results will be easily interpreted in the absence of potential interaction (No significant difference in the time course of response between the 3 languages).

3) The overall difference between M6 and M12 in the change from baseline to assess the sustainability of effect in the overall population. This estimate is interpretable in the absence of interaction between visit and language. In the presence of interaction the difference is not easily interpretable and sustainability will be estimated and tested in the English speaking patients only.

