### 5.7.3. Sustainability of the effect at 12 months

Calculation of change HINT-Q at Month 6/12 = Percent of correct words of HINT-Q at Month 6/12 – Percent of correct words of HINT-Q at 3/6 months

Calculation of change HINT-Q at Month 12-3 = Percent of correct words of HINT-Q at Month 12 – Percent of correct words of HINT-Q at 3 months in case of the change between Month 12 and Month 6 is not significant.

Applicable across language if no effect on language (refer table 12), otherwise applicable only on English-speaking subjects (11.1).

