### **6.3.2. Sustainability of the effect at 12 months in FAS and PPS**

HINT-Q performed at Month 6 in the FAS and PPS sub-group of English speaking patients will be compared to the result at Month 3, and the result at month 12 will also be compared to those obtained at Month 3 and 6 to assess the sustainability of the effect over time.

A one-sided ( $\alpha = 0.025$ ) t-test for paired samples will be used. (refer to tables 11.1 and table 11.2).

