**Figure N (to be done with data in the SAR) : Forest plot of major complications incidence rate**

**Table 10: Assessment of secondary endpoints – Time course of the HINT-Q response – FAS and PPS English speaking patients' sub-group**

Source	Model parameter	df	Sum of squares	Mean Ssquare	F Value	Pr > F	R-Square
Model	Change HINT-Q						
Error	Patient Visit						
Corrected Total							

**Table 11.1 : Assessment of secondary endpoints – Sustainability of the effect of HINT-Q at Month 12 – FAS and PPS English speaking patients sub-group**

	English speaking patients (FAS) N=	English speaking patients (PPS) N=
HINT-Q at baseline – Percent of correct words	x.xx±x.x CI= [x.x;x.x] [xx ; xx] Med=x Missing=x	x.xx±x.x CI=[x.x;x.x] [xx ; xx] Med=x Missing=x
HINT-Q at Month 3 – Percent of correct words	x.xx±x.x CI= [x.x;x.x] [xx ; xx] Med=x Missing=x	x.xx±x.x CI=[x.x;x.x] [xx ; xx] Med=x Missing=x
HINT-Q at Month 6 – Percent of correct words	x.xx±x.x CI= [x.x;x.x] [xx ; xx] Med=x Missing=x	x.xx±x.x CI=[x.x;x.x] [xx ; xx] Med=x Missing=x
HINT-Q at Month 12 – Percent of correct words	x.xx±x.x CI= [x.x;x.x] [xx ; xx] Med=x Missing=x	x.xx±x.x CI=[x.x;x.x] [xx ; xx] Med=x Missing=x
Change at Month 3 (vs baseline) – Percent of correct words	x.xx±x.x CI= [x.x;x.x] [xx ; xx] Med=x Missing=x	x.xx±x.x CI=[x.x;x.x] [xx ; xx] Med=x Missing=x
P value	x.xxx	x.xxx
Change at Month 12 (vs baseline) – Percent of correct words	x.xx±x.x CI= [x.x;x.x] [xx ; xx] Med=x Missing=x	x.xx±x.x CI=[x.x;x.x] [xx ; xx] Med=x Missing=x

P value	x.XXX	x.XXX
Change from M3 to M6 – Percent of correct words	x.XX±x.X CI= [x.X;x.X] [xx ; xx] Med=x Missing=x	x.XX±x.X CI= [x.X;x.X] [xx ; xx] Med=x Missing=x
P value	x.XXX	x.XXX
Change from M3 to M12 – Percent of correct words	x.XX±x.X CI= [x.X;x.X] [xx ; xx] Med=x Missing=x	x.XX±x.X CI= [x.X;x.X] [xx ; xx] Med=x Missing=x-
P value	x.XXX	x.XXX
Change from M6 to M12 – Percent of correct words	x.XX±x.X CI= [x.X;x.X] [xx ; xx] Med=x Missing=x	x.XX±x.X CI= [x.X;x.X] [xx ; xx] Med=x Missing=x
P value	x.XXX	x.XXX

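### Sustainability from month 6 to month 12 is judged by a one-sided test of difference with no stated direction, hypothesis or margin; the estimated change and its two-sided 95% CI should carry the assessment instead

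*Protocol*

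**What the plan says.** The objective appears in two forms. The Protocol Summary (section 1) says: "To show sustainability of the device effect in quiet and in noise in time and after 12 months of use". Protocol 2.4.2 is more specific for HINT-Q: sustainability is to be tested "through the comparison of the scores at month 6 and month 12 in English speaking patients", and possibly in all patients if there is no significant language effect.

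The method is in Protocol 3.6.2.4 b). The month 6 score "will be compared to the result at month 12 to assess the sustainability of the effect over time", by a paired t-test at one-sided alpha 0.025. SAP 6.3.2 keeps that test, adds month 6 against month 3, and says that "the result at month 12 will also be compared to those obtained at Month 3 and 6 to assess the sustainability of the effect". Protocol 3.6.2.4 d) and SAP 6.3.4 carry the HINT-Q analyses over to HINT-N.

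Other relevant text:
- SAP 5.7.3 defines each change as the later score minus the earlier one. It calls for the month 12 minus month 3 change "in case of the change between Month 12 and Month 6 is not significant".
- SAP section 3 prescribes two-sided tests at 5% in general, whereas SAP 6.3.2 is one-sided.
- Protocol 3.6.2.4 c), third contrast, adds an all-language comparison: "The overall difference between M6 and M12 in the change from baseline to assess the sustainability of effect in the overall population". SAP 6.3.3 repeats it.
- SAP Table 11.1 has a row "Change from M6 to M12 – Percent of correct words" with mean, SD, CI and p-value for English-speaking HINT-Q. Table 13 has the equivalent row for HINT-N. Table 12 has no such row for all languages.
- Protocol 3.6.2.4 describes all secondary analyses as supportive estimates and ties labeling claims to the primary analysis alone.

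**The concern.** A one-sided test is not defined until its direction is given. The primary test has written hypotheses and a null value (Protocol 2.4.1.1 and 3.6.2.2; SAP 1.2 and 6.1); the sustainability test has neither. The purpose is to learn whether a gain has been kept, but a test against a null of no difference can only detect a change. Neither possible direction does the job under the course that the protocol itself expects: "After 6 months of CI experience outcomes appear to be stable with the majority of users reaching a performance plateau".

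What is at stake is the wording of the report. Table 11.1 prints a p-value beside the CI, and nothing says which of the two is to be read. A non-significant p-value could be taken as showing that the effect was maintained, when part of the gain may have been lost.

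**Working it through.** **Plan's own figure.** The documents give no sample size, power or margin for sustainability. The only efficacy sample size is the 7 patients for the primary test (Protocol 3.6.1.4: mean 50, SD 25, one-sided 0.025, 95% power). The noncentral t gives power of 97.1% at n=6 and 99.1% at n=7, so 7 is adequate and slightly generous. That calculation concerns a 50-point gain and does not bear on a small change after month 6.

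**Inputs.**
- n=39 English speakers (Protocol 3.6.1.4). As a variant, n=35, from applying to them the 10% loss that Protocol 3.5.4 gives for the whole sample.
- Alpha 0.025, one-sided.
- Score SDs of 22 to 28 points (Protocol 3.6.1.4).
- Correlation r between the month 6 and month 12 scores: not in the documents; assumed 0.5 to 0.9.

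**SD of the difference** = s × √(2(1 − r)).
- s=22, r=0.9: 22 × √0.2 = 9.8
- s=25, r=0.8: 25 × √0.4 = 15.8
- s=28, r=0.5: 28 × √1 = 28.0

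The range used is therefore 10 to 28.

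**Reading 1: the test looks for gain (month 12 above month 6).** With no true change, the chance of significance equals alpha, 2.5%. A truly maintained effect would fail the test in 97.5% of trials. A significant result would, however, exclude a mean loss.

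**Reading 2: the test looks for decline.** The chance of missing a true mean loss L is the probability that a noncentral t with n − 1 degrees of freedom and noncentrality L√n/SD falls below t(0.975, n − 1). Example: L=5, SD=15, n=39 gives noncentrality 5 × 6.245/15 = 2.08 and critical value 2.024, so the loss is missed in 47% of trials.

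**CI half-width** = t(0.975, n − 1) × SD/√n. Example: 2.024 × 15/6.245 = 4.86.

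| SD of difference | 10 | 15 | 20 | 25 | 28 |
|---|---|---|---|---|---|
| 5-point loss missed, n=39 | 14% | 47% | 67% | 77% | 81% |
| 5-point loss missed, n=35 | 18% | 52% | 70% | 79% | 83% |
| 10-point loss missed, n=39 | <1% | 2% | 14% | 32% | 42% |
| 10-point loss missed, n=35 | <1% | 3% | 18% | 37% | 46% |
| 95% CI half-width, n=39 | 3.2 | 4.9 | 6.5 | 8.1 | 9.1 |
| 95% CI half-width, n=35 | 3.4 | 5.2 | 6.9 | 8.6 | 9.6 |

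**Benefit over baseline.** As an illustration, take the planned 50-point gain at month 6 as given and suppose that the observed change afterwards is zero. The widest half-width in the table still leaves 50 − 9.6 = 40.4 points.

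**Consistency of the SAP.** SAP 5.7.3 makes the month 12 minus month 3 change conditional on a non-significant month 6 to month 12 result; SAP 6.3.2 makes that comparison unconditionally. Protocol 3.6.3.1 limits the imputation rules to the primary analysis, whereas SAP section 3 lists them under the general approach. If Rule 1 were applied here, a missing month 6 score would take the month 12 value and that patient's difference would be zero. Each such patient among 39 would pull the mean change toward zero by 1/39 = 2.6%.

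**The case against.** The strongest reply is that little is missing. The secondary analyses are declared supportive estimates, the CI for the change is already in Tables 11.1 and 13, and no labeling claim is involved. All of that stands. It limits the importance of the point and favours the fix, since an estimate is best read through its interval.

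A reader might go further than the documents allow in four ways.
- *The plan will call a non-significant result sustained.* Neither document says so. SAP 5.7.3 uses non-significance only to trigger another calculation. The gap is that no rule of interpretation is given.
- *The p-value can never be informative.* A significant gain would exclude a mean loss. It is merely unlikely under a plateau.
- *The test has little chance of detecting any relevant loss.* That holds only for losses of about 5 points at the larger assumed SDs. With n=39, a 10-point loss is detected in 58% to over 99% of trials, and a 20-point loss is missed in under 1% even at SD 28. The documents do not say what size of loss matters; their 20 points refer to improvement from baseline.
- *Sustainability means only month 6 against month 12.* Protocol 2.4.2 says this for HINT-Q, but the Summary is broader, and month 12 against baseline also addresses it.

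It is also fair to object that the correlation is assumed and moves the result a great deal, and that 39 is not fixed because languages may substitute for one another. Finally, the imputation point is a conflict of scope between the two documents. It does not show that Rule 1 will be applied here.

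**Conclusion.** The concern holds in limited form. The specified test cannot answer the question set for it: under the expected plateau one direction is significant in 2.5% of trials, and in the other a non-significant result is not evidence of maintenance. For a decline test with 39 patients and an assumed SD of the difference of 10 to 28 points, a true mean loss of 5 points is missed in 14% to 81% of trials and one of 10 points in under 1% to 42%. The interval, with a half-width of about 3.2 to 9.1 points, shows directly which losses remain compatible with the data. The logical point does not depend on the assumed SD; the percentages do.

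The consequence is confined to a supportive secondary objective for HINT-Q and HINT-N. The primary conclusion and the judgement of benefit over baseline at month 12 are unaffected. This should be changed, but it does not threaten the trial's main result.

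**What to change.** In SAP 6.3.2:
- Replace the one-sided p-value as the basis for the assessment with the estimated month 12 minus month 6 change and its two-sided 95% CI, from Table 11.1 for HINT-Q and Table 13 for HINT-N in English speakers.
- State that a non-significant difference will not be reported as sustained.
- Treat the all-language contrast in SAP 6.3.3 the same way, and add a row for it to Table 12.
- Say what the month 12 minus month 3 change is for, and make SAP 5.7.3 and 6.3.2 agree on whether it is conditional.
- Use only patients with both scores observed, so that Rule 1 does not enter this comparison.

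Reading the CI also removes the clash with the two-sided convention in SAP section 3.

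The cost is a few sentences and one table row, with no new data. The price is that no formal claim of sustainability is made. Such a claim would need a non-inferiority margin. None is proposed here because the documents give no basis for one. The trial is open label, its planned completion was December 2019 and SAP version 3.0 is dated 27/01/2020, so a margin set now could be seen as informed by the data.

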**c) Difference in the time course of HINT-Q responses across languages**

The FAS including all patients instead of the subset of English speaking patients will be used in these secondary analyses. A mixed model for repeated measures will be fitted using the change from baseline to M3, M6 and M12 in the HINT-Q score as the responses and the following covariates or terms: the visit (M3, M6 and M12, fixed effect), the patient (random effect), the language (fixed effect) and the interaction between visit and language. The variance covariance matrix will be unstructured. If the p value of the interaction is below 0.15 then a signal of potential interaction is detected and the time course of speech performance is possibly dependent upon the language. Regardless the p value of interaction a graph will present the time course of the response for each language.

A series of contrasts will be performed to estimate and test:

1) The difference between languages in the change from baseline at each time point.

The estimate and test at M6 will be the most supportive result.

2) The overall mean change from baseline at each time point. The test against no change will be performed. Results will be easily interpreted in the absence of potential interaction (No significant difference in the time course of response between the 3 languages).

3) The overall difference between M6 and M12 in the change from baseline to assess the sustainability of effect in the overall population. This estimate is interpretable in the absence of interaction between visit and language. In the presence of interaction the difference is not easily interpretable and sustainability will be estimated and tested in the English speaking patients only.

**d) Analysis of HINT-N**

All analyses performed on the HINT-Q will be performed on the HINT-N, the response will be the change from baseline.

**e) Measures of impedance**

The time course of electrodes impedance performed at each time points will be analyzed through a mixed model for repeated measure and contrasts of interest will be described in the SAP.

**f) ECAP**

ECAP measures amplitude between (N1-P2) peaks. Measures will be performed over time from baseline to 12 months. The times course of the response will be fitted to a mixed model for repeated measures and contrast of interest will be describes in the SAP.

### **g) Safety analysis**

The incidence rates of 1) minor complications, 2) any complications and 3) any adverse events will be estimated with their 95% C.I. in the safety population. The time to the first minor or major complications will be investigated through Kaplan Meier survival (event free) analysis and the graph of the estimated event free probability by the time will be presented.

A breakdown of all adverse events by categories will be done. The occurrence rates and 95% CI within each category will represent the safety profile of the new device. The observed rate in previous generations of device will be provided as a yard stick if they are available. Results from safety assessments will be presented in a tabular and/or graphical format (Forest plot).

Data regarding the average surgical time will also be reported.

### **h) Handling of site effects**

The site effect is partly confounded with the language effect. Consequently the site effect will be investigated in English speaking patients. An analysis of variance using the change from baseline to M6 as the response and the site as covariate will be performed. If the site effect is significant, then the mean change from baseline to M6 is dependent upon the site. Regardless the p value of ANOVA a Forest plot presenting the mean change from baseline to M6 of each site along with the 95% confidence interval will be presented to verify whether there is just a quantitative difference across sites or a qualitative one. In case of significant site effect and qualitative difference the site with the largest mean deviation from the overall mean change from baseline will be removed from the sample to estimate the overall mean change from baseline in the remaining sites.

### **3.6.3 Handling of Missing Data**

#### **3.6.3.1 Imputation rules used in the primary analysis**

Rule 1: If the assessment at M6 is missing but a further assessment is available the missing assessment will be replaced by the next available data.

Rule 2: If the assessment at M6 and M12 is missing but the assessment at M3 is available then M3 score will be carried forward.

Rule 3: If the assessment at M6 and M12 is not available in quiet conditions but available in noise then the score at M6 in noise will be used.

Rule 4: In case of lost to follow-up or withdrawal of the informed consent for unknown reason a stochastic regression imputation will be used.

Rule 5: In case of withdrawal not due to a failure of the implantation or complications the baseline will be imputed at month 6.

Rule 6: In case of withdrawal due to major complications requiring new implantation the worst score (0%) will be imputed.

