#### **At visit 2 (preoperatively)**

The test is conducted in quiet and in noise background, and in the best-aided conditions

In quiet:

The subject's is given practice sentences to become familiar with the task before each test. Then two 20-sentences lists of HINT shall be presented to the subject, in front (0° azimuth), in quiet at a conversational speech level of 60 dB SPL (Appendix 9: Calibration considerations). All words in the sentence repeated correctly, (Nilsson et al. 1994 [5]) shall be computed to calculate a score in percent correct of total words.

In noise:

As described above, the same procedure is applied for HINT-N, sentences are presented at +10dB SNR, with noise set at 55 dB SPL, and signal at 65 dB SPL.

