**a) HINT in Quiet (HINT-Q)**

The primary efficacy endpoint of the Neuro CIS is assessed with the HINT score in quiet in the ipsilateral ear. The primary endpoint is the difference between the baseline performance in the best-aided condition and the performance in the implanted ear within 6 months following activation. The mean score of words correctly repeated in quiet will be used as the primary outcome measure for assessing the primary benefit.

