## 3. General statistical approach

The quantitative variables will be summarized using the following parameters:

- Number of missing and non-missing data,
- Mean and Standard deviation,
- 2-sided 95% Confidence Interval (CI) of the mean,
- Median, minimum and maximum.

The qualitative variables will be summarized using the following parameters:

- Number of missing and non-missing data,
- Counts and percentages with 2-sided 95% CI.

Statistical analysis will be performed at the 5% global significance level using 2-sided tests.

Statistical tests will be chosen according the type of variable:

By default, missing data or unknown responses will not be counted in the denominator of percentages but will be presented in the results tables.

Handling of missing data:

- Rule 1: If the assessment at M6 is missing but a further assessment is available, the missing assessment will be replaced by the next available data.
- Rule 2: If the assessment at M6 and M12 are missing but the assessment at M3 is available then M3 score will be carried forward.
- Rule 3: If the assessment at M6 and M12 is not available in quiet conditions but available in noise then the score at M6 in noise will be used.
- Rule 4: In case of lost to follow-up or withdrawal of the informed consent for unknown reason a stochastic regression imputation will be used. This technique computes a regression equation that generates predicted values for the missing data. After a random error term generated from a normal distribution (with a mean of zero and a variance equal to the residual variance from the preceding regression analysis) is added to each predicted score and the resulting sum is used in place of missing values.
- Rule 5: In case of withdrawal not due to a failure of the implantation or complications the baseline will be imputed at month 6.
- Rule 6: In case of withdrawal due to major complications requiring new implantation, the worst observed score will be imputed.

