## 5.6. Primary end point

### 5.6.1. HINT in Quiet at Month 6

Change from baseline to month 6 (refer to table 8).

Calculation = HINT-Q at Month 6 - HINT-Q at Inclusion visit

The primary efficacy endpoint of the Neuro CIS is assessed with the HINT score in quiet, on the ipsilateral ear.

The mean HINT scores in quiet will be used as the primary outcome measures for assessing the primary benefit.

The primary analysis will be performed on a subgroup of the FAS which consists of all English-speaking patients (Exclusion of Danish and French-Canadian speaking patients). The analysis will be replicated in PPS.

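### Imputation Rule 3 fills a missing quiet score with a noise score, so the imputed change does not measure the primary endpoint

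*Protocol*

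**What the plan says.** Protocol 3.6.1.1 a) fixes the outcome: "The mean score of words correctly repeated in quiet will be used as the primary outcome measure". SAP 5.6.1 gives the formula: "Calculation = HINT-Q at Month 6 - HINT-Q at Inclusion visit".

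Rule 3 stands in Protocol 3.6.3.1, headed "Imputation rules used in the primary analysis", and again in SAP section 3. It applies when the quiet score is missing at both month 6 and month 12. The Protocol version ends: "then the score at M6 in noise will be used". The SAP version ends: "available in noise then the score at M6 in noise will be used". Neither document adds a conversion, a choice of baseline or a reason.

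Protocol 3.5.5.1 b describes two different tests. HINT-Q is presented "in quiet at a conversational speech level of 60 dB SPL". For HINT-N, "sentences are presented at +10dB SNR, with noise set at 55 dB SPL, and signal at 65 dB SPL". Protocol 3.6.1.2 b) lists HINT-N as a secondary criterion with its own preoperative measurement.

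Two neighbouring rules matter. Rule 2 carries the month 3 score forward when month 6 and month 12 are missing. Rule 4 uses stochastic regression imputation, but only after loss to follow-up or a consent withdrawal with no known reason. Neither document states an order among the six rules.

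**The concern.** A change score needs the same measurement at both ends. Rule 3 takes the later value from a different test, so the imputed change reflects the difference between the test conditions as well as the effect of the device. That value then enters the primary mean as if it were a quiet score. Mock Table 8 in the SAP has rows for HINT-Q only, so it would also be reported as one.

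What is at stake is the estimated mean change, the SAP 6.1 count of patients gaining at least 20 points, and reproducibility. If more than one rule can be read to fit a patient, the choice in an open-label, single-arm trial may be made with the scores in view.

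**Working it through.** **The plan's own figure.** Protocol 3.6.1.4 states 7 patients for 95% power: one-sample t-test, one-sided 0.025, mean change 50, SD 25. With noncentrality (50/25)√n, exact power is 90.9% at n = 5, 97.0% at n = 6 and 99.1% at n = 7. Seven therefore meets the target, and six would. This confirms the inputs used below; the point itself does not depend on it.

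**What Rule 3 puts into the endpoint.** Write Q0 and Q6 for the quiet scores at inclusion and month 6, and N0 and N6 for the noise scores.

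- Endpoint: Q6 − Q0.
- Rule 3 with the SAP 5.6.1 formula left as it stands: N6 − Q0. The error is N6 − Q6 = −g, where g = Q6 − N6.
- Rule 3 with the noise baseline subtracted instead: N6 − N0. The error is −(g − g0), where g0 = Q0 − N0. This is consistent within the patient but is still a change in noise.

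Rule 3 does not say which baseline applies. The first form is inferred from the formula.

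**Effect on the mean.** Inputs: 39 English-speaking patients (Protocol 3.6.1.4); k patients imputed by Rule 3 and gap g, both assumed because the documents give neither. With the HINT-Q baseline, the shift is −(k/39) × g. Sizes in points:

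| k | gap 10 | gap 20 | gap 40 |
|---|---|---|---|
| 1 | 0.26 | 0.51 | 1.03 |
| 2 | 0.51 | 1.03 | 2.05 |
| 4 | 1.03 | 2.05 | 4.10 |
| 8 | 2.05 | 4.10 | 8.21 |

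The shift is downward if noise scores are lower than quiet scores and upward if they are higher.

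**Effect on the test.** Take the extreme case k = 8, g = 40. The mean is 50 − 8.21 = 41.79. With p = 8/39, the SD is √(25² + p(1 − p) × 40²) = √(625 + 260.9) = 29.76. The expected t is 41.79/29.76 × √39 = 8.77. Power against a null of zero stays essentially 100%.

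**Effect on the responder count.** If g is positive, a patient whose true quiet change lies between 20 and 20 + g is counted as a non-responder; if g is negative, the reverse can happen. One reclassified patient moves the rate by 1/39 = 2.6 percentage points on a denominator of 39.

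**Rules 2 and 3 side by side.** Rule 2 speaks of a missing assessment; Rule 3 speaks of quiet being unavailable and noise available. If the assessment in Rule 2 means the quiet score, a patient with quiet at month 3, noise at month 6 and no later quiet score meets both rules and could be given either value. If it means the whole visit's testing, the rules do not overlap. The text does not settle which. Rule 3 also supplies no value when noise is available only at month 12.

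**The case against.** **The rule will hardly ever apply.** Both tests are scheduled at the same visits (Protocol 3.5.5.4), and quiet must be missing twice while noise exists at month 6. Appendix 7 narrows this further: a patient with no words correct on the first six quiet sentences is recorded as 0 on both tests, so is not missing. This stands and limits the importance of the point.

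**The conclusion cannot change.** This also stands, as the extreme case shows. A reader might infer a threat to the primary test; the plan's own effect and SD rule that out.

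**The sensitivity analyses already cover it.** Only in part. The best case deletes patients without month 6 and month 12 data and the worst case imputes 0. Neither uses noise scores, but neither isolates Rule 3. Deletion is not an upper bound either: a substituted change above the mean of the other patients would give a higher result. The tipping-point analysis includes the primary rules as a step.

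**The rules are numbered, so they can be read in sequence.** That is possible but not stated. It would have an odd result elsewhere: a patient withdrawn after month 3 for a major complication requiring a new implant would take the month 3 score under Rule 2 and never reach the worst-score Rule 6.

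**Substituting a noise score is at least conservative.** A reader might infer this, but the documents do not establish it. They report no HINT-N results. Protocol 3.5.5.1 sets speech 5 dB higher in the noise test (65 against 60 dB SPL), while Appendix 9 says all HINT tests run at 60 dBA, and these statements must be reconciled. Appendix 7's recording of 0 in noise after 0 in quiet fits noise being harder, but only at the floor and without giving a gap.

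**Conclusion.** The point holds as a matter of definition. As written, Rule 3 puts a value from a secondary test into the primary endpoint without conversion or a named baseline. The size is small: about 0.3 to 1.0 point on the mean per affected patient, assuming 39 patients, a gap of 10 to 40 points in either direction and the HINT-Q baseline, plus a possible change of one in the 20-point responder count. Few such patients are expected.

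Two stronger readings go beyond the text. The plan does not state that the imputed change is noise minus the quiet baseline; that follows only when Rule 3 is joined to the SAP 5.6.1 formula. Nor is a clash between Rules 2 and 3 established; it depends on how the assessment in Rule 2 is read. What is established is the substitution of the wrong test, the unnamed baseline and the unstated order. This is worth correcting but is minor.

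**What to change.** In Protocol 3.6.3.1 and SAP section 3:

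1. Delete Rule 3.
2. State that Rules 1 and 2 refer to the HINT-Q score, so that an available quiet score at month 12 or month 3 is used.
3. Extend the Rule 4 regression imputation to patients who attended but have no quiet score after activation. List its predictors, which the SAP does not do now, and allow HINT-N only as one of them.
4. State the order in which the remaining rules apply, including for a patient who meets both Rule 2 and Rule 6.

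Step 3 is needed because Rule 4 as written would not cover a patient who attended month 6 and completed only the noise test. Without it, deleting Rule 3 would leave such a patient with no rule if there is no quiet score at month 3, 6 or 12.

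The cost is a small widening of Rule 4, which is a change of method as well as of wording. No further data or patients are needed. One weakness remains: a month 3 score carried forward may understate month 6 if scores are still rising. No corrected estimate can be given, because the documents report no HINT-N mean, SD or correlation with HINT-Q.
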